## 1.0 Background

COVID-19 infections caused by SARS-CoV-2 have overwhelmed health care systems around the globe due to the profound respiratory failure that is characteristic of severe disease and which constitutes the primary reason for death. Immune responses to SARS-CoV-2 infection follow a two phase pattern. In the first phase, adaptive immune responses are protective and lead to mild disease. However, if immunity is impaired or otherwise deficient, severe cases are associated with Lymphopenia and a cytokine storm at which point the immune response is maladaptive and leads to acute respiratory distress syndrome (ARDS) and pulmonary failure.

COVID-19 is a Coronavirus that is similar to the pathogen (SARS-CoV) which caused the SARS epidemic of 2002-2003. Research into SARS-CoV demonstrated the potential role of TMPRSS2 in the pathogenicity of that disease and in particular the link to pulmonary manifestations. Previous work has shown that the SARS S (spike) protein is proteolytically processed by TMPRSS2. SARS S is cleaved into several fragments upon coexpression of TMPRSS2 (cis-cleavage) and upon contact between SARS S-expressing cells and TMPRSS2-positive cells (trans-cleavage). SARS S protein is associated with inhibition of antibody mediated neutralization of the virus, and thus promotes viral spreading. TRMPSS2 is also a coreceptor for SAR-CoV (with ACE2), and is thus associated with SARS-CoV infectivity, shedding, and resistance to protective antibodies. Like SARS, SARS-CoV-2 has been shown to use the ACE2 and TMPRSS2 receptors for cell entry.

Camostat is a serine protease inhibitor that is currently approved in Japan for the treatment of chronic pancreatitis and reflux esophagitis. It exhibits anti TMPRSS2 activity in cell line studies. Camostat successfully abrogated SARS S cleavage, inhibited cell entry, and decreased viral replication.

There is currently no proven therapy for COVID-19 infection. Multiple trials are currently active, with multiple agents having shown some promise based on small case series. These include hydroxychloroquine and azithromycin.

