#### 13.4 Planned Analyses

##### Primary Analysis

Frequency distributions and chi-square tests will be used to screen for major imbalances in the two randomization groups for qualitative variables; graphical displays including box plots and summary statistics (e.g., mean, median, standard deviation, ranges, etc.) will be used for quantitative variables with t-tests (after appropriate transformations if necessary to meet the assumptions of the methods).

The primary outcome will include the number of patients who are alive AND free from respiratory failure at Day 28 divided by the total number of patients in each arm. This endpoint will be analyzed in a binary fashion using properties of the binomial distribution and will be compared between randomized arms by the use of independent samples Z-test for proportions and a 95% confidence interval will be constructed for the difference between arms. Proportions will also be compared using Cochran-Mantel-Haenszel tests, including the stratification factors of age and baseline disease severity. Multivariable logistic regression models will be used to assess the influence of treatment while controlling for covariates of interest (gender, symptom onset, comorbidities) along with stratification factors. Primary analysis for this efficacy outcome will include all participants who are randomized and received at least 1 dose of study treatment. Participants will be analyzed according to the treatment to which they were randomized.

Efforts to minimize loss to-follow-up will be considerable. However, small amounts of missing data may occur. In such cases, participants without Day 28 outcome data will be excluded from the analysis. Sensitivity analyses will evaluate the impact of making different assumptions about the missing observations.

**Interim analyses:** Two interim analyses will be conducted after 25% and 50% of patients have completed the 28 day study period. The interim analysis will include the below stopping rules for efficacy and futility based on a Lan-DeMets spending function with O'Brien-Fleming boundaries. Occurrence of adverse events will also be evaluated at the interim analysis.

Accrual	Control arm (#)	Camostat arm (#)	Total number (#)	Efficacy boundary (Z scale)	Alpha spent	Futility boundary (Z scale)	Beta spent
25%	33	33	66	+/- 4.33	0.001	+/- 0.007	0.002
50%	66	66	132	+/- 2.96	0.003	+/- 0.34	0.04
100%	132	132	264	+/- 1.97	0.05	+/- 1.97	0.20

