**5. Length of Stay:** Length of stay will be defined as the time from study entry until the time of hospital discharge and the number of days hospitalized will be compared between groups by use of non-parametric Wilcoxon rank-sum test. The proportions of patients who require an ICU admission will be compared between randomized groups by the use of independent samples Z-test for proportions and a 95% confidence interval will be constructed for the difference between groups. In addition, time in the ICU will be described in number of days spent receiving ICU care, if applicable.

**6. Duration of Mechanical ventilation / ECMO:** Duration of ventilator / ECMO use will be summarized by medians or quartiles by arm for those subjects who have a baseline score of 6-7 at study entry.

**7. Duration of non-invasive ventilation / high-flow oxygen:** Duration of non-invasive ventilation / high-flow oxygen will be summarized by medians and quartiles by arm for those patients who have a clinical status score of 5 at study entry.

**8. Duration of supplemental oxygen use:** Duration of supplemental oxygenation use will be summarized by medians and quartiles by arm for those patients who have a clinical status score greater than or equal to 4 at study entry.

**9. Occurrence of adverse events related to treatment:** Analyses for safety will include all participants who are randomized and received at least 1 dose of study treatment.

Participants will be grouped according to the treatment to which they were randomized. Events will be summarized on the basis of the date of onset for the event. The maximum grade for each type of adverse event will be recorded for each patient. Frequency tables of adverse events will be constructed based on maximum grade for each treatment arm. Overall adverse event rates, rates of grade 3 or higher events and serious adverse events will be compared between treatment groups using Chi-square or Fisher's exact test.

**10. Development of thrombosis / bleeding complications:** Incidence of arterial and venous thrombosis or bleeding complications will be described and compared by treatment arms by use of chi-square or Fisher's exact test.

Subgroup analyses for the primary and secondary analyses will examine the treatment effect across the following subgroups of interest. Forest plots with odds ratio and 95% confidence intervals will be presented along with interaction tests.

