- Duration of symptoms prior to enrollment: <= Median versus > Median number of days,
- Comorbidities, presence of Hypertension/CHF/COPD/coronary artery disease: Yes versus No,
- Age: <65 versus >= 65 years,
- Sex: Female versus Male,
- Baseline severity of disease: Mild/moderate versus Severe disease

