### 13.6 Sample Size

Randomization will be done according to a 1:1 ratio. Based on data from Wang et al, 82% of patients treated with Remdesivir were alive and free from respiratory failure at day 28. In the preliminary report of Remdesivir for the treatment of COVID-19 in 1059 hospitalized patients, approximately 70% of patients treated with Remdesivir were alive and free from respiratory failure at Day 15; Day 28 data are not yet available. Using an expected proportion of 80% for the SOC control arm, this study would require 132 patients in each arm (total of 264 patients). Sample sizes of 132 in each arm achieves 80% power to detect a difference between the group proportions of 12% for the primary endpoint. The proportion in the treatment arm is assumed to be 80% under the null hypothesis and 92% under the alternative hypothesis. The proportion in the SOC arm is 80%. The test statistic used is the two-sided Z-Test with unpooled variance. The significance level of the test is 0.05 (two-sided).

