### 13.9 Inclusion of Women and Minorities

13.9b This study will be available to all eligible patients, regardless of race, gender, or ethnic origin.

13.9c There is no information currently available regarding differential effects of this regimen in subsets defined by race, gender, or ethnicity, and there is no reason to expect such differences to exist. Therefore, although the planned analysis will, as always, look for differences in treatment effect based on racial and gender groupings, the sample size is not increased in order to provide additional power for subset analyses.

13.9d The geographical region served by Mayo Clinic has a population which includes approximately 30% minorities. Based on the burden of COVID in our community, we expect about 30% of patients will be classified as minorities by race and about 40% of patients will be women. Expected sizes of racial by gender subsets are shown in the following table:

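### The only planned test of effect modification by symptom duration splits days at the trial's own median; a prespecified continuous interaction would use the data better if modification is gradual

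*Combined protocol and SAP*

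**What the plan says.** Section 13.5 lists five subgroup factors for the primary and secondary analyses. One is symptom duration, defined as "Duration of symptoms prior to enrollment: <= Median versus > Median number of days". For these subgroups, "Forest plots with odds ratio and 95% confidence intervals will be presented along with interaction tests".

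Symptom timing appears in one other analysis. The multivariable logistic model in Section 13.4 estimates the treatment effect while "controlling for covariates of interest (gender, symptom onset, comorbidities) along with stratification factors". There it is an adjustment covariate. Its coding is not stated, and no product term with treatment is planned.

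No section plans a continuous, spline or fixed-day interaction for duration. Duration is not a stratification factor (Section 5.0), and the eligibility criteria (Section 3.0) set no limit on it. The nearest biological rationale is in Section 1.0: "Immune responses to SARS-CoV-2 infection follow a two phase pattern". On power, Section 13.9 says, of race and gender subsets, that "the sample size is not increased in order to provide additional power for subset analyses".

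**The concern.** The subgroup is defined in days, so the trial will hold duration as a number and then reduce it to two groups for the test. If benefit from an inhibitor of viral entry fades gradually with time since onset, a two-group comparison ignores all variation within each half. Interaction tests in a trial of this size have little power to begin with, so avoidable loss matters to anyone who hopes to learn from this analysis.

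A second, smaller point is that the cut in days is unknown until enrolment ends. Other trials will have other medians, so early and late here will not mean the same as early and late elsewhere.

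What is at stake is how informative one exploratory subgroup analysis is. The primary conclusion does not depend on it.

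**Working it through.** **1. The plan's own figure.** Section 13.6 assumes 80% in the control arm and, for the treatment arm, "80% under the null hypothesis and 92% under the alternative hypothesis", at two-sided 0.05 with an unpooled Z-test and 132 per arm.
- Variance sum: 0.80×0.20 + 0.92×0.08 = 0.2336.
- n = 0.2336 × (1.960 + 0.842)² / 0.12² = 127.3, so 128 per arm. Power at 132 per arm is 81.4%.
- The pooled formula gives 131 per arm and 80.6% power.

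The stated 132 per arm and 80% power are consistent with this. The documents give no power figure for any interaction.

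**2. Precision of the planned split.** Assume equal halves (66 per arm in each), the design rates in both halves and no missing outcomes.
- Expected failures: 132×0.20 + 132×0.08 = 37.
- Variance of the log odds ratio in one half: 1/(66×0.16) + 1/(66×0.0736) = 0.3006.
- SE of the difference between halves: √(2×0.3006) = 0.775.
- Ratio of odds ratios detectable with 80% power: exp(2.80×0.775) ≈ 8.8.

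The overall design odds ratio is (0.92/0.08)/(0.80/0.20) = 2.875, so only very strong modification is detectable.

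**3. Information lost by the split if modification is linear.** The share retained, relative to a linear term, is approximately the squared correlation between duration X and its median-split indicator. With equal halves this is Δ²/(4 Var X), where Δ is the difference in mean duration between the halves. The distributions are assumptions.

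| Assumed duration | Retained | Lost |
|---|---|---|
| Uniform | 0.25/(4/12) = 0.75 | 25% |
| Normal | 2/π = 0.637 | 36% |
| Gamma, shape 4 | 0.593 | 41% |
| Gamma, shape 2 | 0.553 | 45% |
| Exponential | (ln 2)² = 0.480 | 52% |
| Lognormal, log-SD 0.4 | 0.557 | 44% |
| Lognormal, log-SD 0.6 | 0.470 | 53% |
| Lognormal, log-SD 0.8 | 0.370 | 63% |

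The lognormal rows use (2Φ(σ) − 1)²/(exp(σ²) − 1). Rounding to whole days gives losses of about 25% to 50% for typical values near 7 days. Because ties go to the lower group, 38% to 50% of patients then fall above the median.

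The skewed rows assume an effect linear in raw days. If duration is lognormal but the effect is linear in log days, log duration is normal and the loss is 36%.

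**4. Power of the interaction test.** Logistic regression was simulated with N = 264, 3,000 runs per setting and a Wald test at 0.05. Control success was 80% at every duration, and the odds ratio at average duration was 2.875. Whole-day durations were normal (mean 7, SD 3), gamma (mean 7, SD 4) or uniform (1 to 14). The slopes are assumptions.

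| True modification | Duration | Split | Linear term |
|---|---|---|---|
| None | all three | 3–4% | 4–5% |
| Linear, 0.5 log-OR per SD | normal / gamma / uniform | 15 / 16 / 15% | 24 / 31 / 23% |
| Linear, 1.0 log-OR per SD | normal / gamma / uniform | 51 / 53 / 51% | 74 / 83 / 71% |
| Step at median, ±0.5 log-OR | normal / gamma / uniform | 21 / 18 / 17% | 18 / 13 / 17% |
| Step at median, ±1.0 log-OR | normal / gamma / uniform | 57 / 53 / 50% | 48 / 38 / 53% |

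**5. A spline instead.** For a truly linear trend with normal duration, set the effect so that the linear term has 30% power. Noncentral chi-square calculations then give 21% for the split, 23% for a spline interaction with 2 degrees of freedom and 20% for one with 3. Extra degrees of freedom use up most or all of the gain.

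**The case against.** The strongest reply is that the split can be the better test. Section 1.0 speaks of two phases. It does not tie them to days of symptoms or describe a gradual change, and a two-phase process fits a step at least as well as a straight line. With a step at the median, the split has more power than a linear term for normal and gamma durations (step 4). This stands and makes the recommendation conditional. It does not reverse it, because nothing in the documents places a biological change at whatever this trial's median turns out to be.

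Three stronger readings are tempting, and the documents do not support them.
- A reader might infer that the split simply discards a third to a half of the information. That holds only for linear modification with roughly normal to exponential or moderately lognormal durations. The range examined runs from 25% to 63%, and the loss is zero for a step at the median. The highest figures also assume an effect linear in raw days, so they do not describe what a log-days term would recover.
- A reader might infer that the sponsor treats duration as a key modifier. The documents never say so. It is one of five subgroup factors and is not stratified.
- A reader might infer that a cut taken from the data inflates the false-positive rate. It does not. The rule is fixed in advance and uses a baseline value, not outcome or arm. Only comparability across trials suffers.

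It is also fair to say that the practical consequence is small. The analysis is exploratory in practice, and with about 37 failures no coding makes moderate modification reliably detectable.

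**Conclusion.** The point holds as a low-cost improvement. The median split is the only planned test of modification by symptom duration, and it coarsens a value that the trial holds in days. If modification is linear on the log-odds scale, the information lost is about 25% (uniform), 36% (normal), or about 50% or more (strongly right-skewed, effect linear in raw days). On the same assumption, a linear term raises power from about 15% to 23–31% at 0.5 log-OR per SD, and from about 51–53% to 71–83% at 1.0 per SD. If modification is a step at the median, the split loses nothing and the linear term can be weaker.

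These sizes rest on assumed distributions, slopes and shapes, because the documents supply none. The primary test, its type I error and the sample size of 264 are unaffected.

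**What to change.** In Section 13.5, name as the interaction test for this factor a single treatment-by-duration product term, with one degree of freedom, in the logistic model already planned in Section 13.4. Enter duration as days, or as log days if the pooled, blinded baseline distribution is skewed. Fix the form, and the handling of zero days if logs are used, before unblinding. Keep the median split for display in the forest plot and report the cut in days.

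This needs no new data, visits or patients. The costs are that a functional form must be chosen in advance, that power falls if the true effect is a step near the median, and that the test stays underpowered for moderate modification. The report should therefore not read a non-significant interaction as evidence of a uniform effect. A spline with several degrees of freedom is not recommended as the test, since it may gain little over the split.

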#### Exploratory Analysis

**Time to Viral Clearance:** Viral clearance will be assessed at days 1,7, 14, 28 and 56 after study entry and the viral clearance rate at each of these days will be estimated as the proportion of patients who are documented as having non-detectable viral shedding divided by the total number of patients in that treatment arm. The rates at each time point will be compared using chi-square tests to assess differences between treatment arms

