- e. Targeted physical examination will specifically target the pulmonary system, as well as any areas of concern from the medical history or noted on the prior physical examination or indicated by subject systems or other findings as determined by the Investigator or designee.
- f. BP, pulse rate, respiration rate, and temperature. Vital signs will be measured at Baseline, and twice daily at least 8 hours apart while hospitalized, and once daily as an outpatient. Timing of assessments in accordance with institutional SOP for hospitalized patients.
- g. See Appendix I for a list of specific CBC with differential, comprehensive metabolic panel, renal profile, and urinalysis with microscopic tests.
- h. See Section 12.0 for description of scale.
- i. Collect nose or throat swab to measure for the presence or absence of SARS-CoV-2 by a PCR based COVID-19 test. The swabbing site (nose or throat) used for the Baseline evaluation should be maintained for all subsequent assessments of the study. If only one nostril will be sampled, use the same nostril for collections.
- j. SpO2 determined by pulse oximetry with simultaneous recording of FiO2 to be recorded twice daily at least 8 hours apart while hospitalized, and once daily as an outpatient. Timing of assessments in accordance with institutional SOP for hospitalized patients.
- k. A + 3 day window will be allowed.
- l. Patients who are discharged prior to Day 14 will not need to come into the clinic to follow Day 1-14 Test Schedule. Patients will be called by Study Team for remote evaluation and will resume visits on Day 14 unless needing to be seen sooner.
- m. Assess as clinically indicated by the treating physician.
- n. Stool samples can be  $\pm$  1 day and will be collected only if patient is able to produce.
- o. Since patients may improve and be discharged from the hospital at any point during the study period, remote monitoring without an in-person exam may be utilized for all Physical exam and assessments after day 1 in accordance with institutional SOP.

R Research Funded

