## 9.0 Biospecimens

### 9.1 Summary Table of Research Blood/Blood Products to Be Collected for This Protocol

	Specimen Purpose	Mandatory or Optional	Blood or Body Fluid being Collected	Type of Collection Tube (color of tube top)	Volume to collect per tube (# of tubes to be collected)	Day 1	Day 7	Day 14	Day 28	Day 56	Process at site? (Yes or No) 
-C1	 Correlative  Banking	Mandatory on day 1, optional all other days	Nasal Pharyngeal	Swab	1	X	X	X	X	X	N
-C2	 Correlative  Banking	Mandatory on day 1, optional all other days	Whole blood	SST (red and black marble top)	8.5mL (1)	X	X	X	X	X	N
C3 	 Correlative  Banking	Mandatory on day 1, optional all other days	Stool	Brown and white bottle	25mL	X	X	X	X		N
-C4	 Correlative  Banking	Mandatory on day 1, optional all other days	Saliva	Oragene	1	X	X	X	X		N

	Specimen Purpose	Mandatory or Optional	Blood or Body Fluid being Collected	Type of Collection Tube (color of tube top)	Volume to collect per tube (# of tubes to be collected)	Day 1	Day 7	Day 14	Day 28	Day 56	Process at site? (Yes or No) 
-C5	 Correlative  Banking	Mandatory on day 1, optional all other days	PBMC, plasma	Na Heparin (green top)	10mL	X				X	N

1. All samples will be processed and stored by Arizona BAP.
2. All Mayo sites using RLIMS must add MCA processing instructions to RLIMS builds.
3. Stool samples can be  $\pm$  1 day and will be collected only if patient is able to produce.

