### 13.3.3 Exploratory Endpoint(s)

**1. Time to Viral Clearance:** Viral clearance will be assessed at days 1, 7, 14, 28, 56 after study entry and the proportion of patients having viral clearance at each of these days will be estimated as the proportion of patients who are documented as having non-detectable

viral shedding divided by the total number of patients in each treatment arm. Serum and nasopharyngeal assays will be used for this analysis.

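### Exploratory viral clearance is divided by all patients in the arm although later samples are optional, so an unsampled patient counts as not cleared

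*Combined protocol and SAP*

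**What the plan says.** Two places give the same formula. Section 13.3.3 (Exploratory Endpoints) takes patients documented as having non-detectable "viral shedding divided by the total number of patients in each treatment arm", at Days 1, 7, 14, 28 and 56. The Exploratory Analysis text in Section 13.5 repeats it: the count of patients with a documented non-detectable result is "divided by the total number of patients in that treatment arm". The comparison is made visit by visit: "The rates at each time point will be compared using chi-square tests to assess differences between treatment arms".

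On the source of the result, Section 13.3.3 says "Serum and nasopharyngeal assays will be used for this analysis". The specimen table in Section 9.1 labels the nasopharyngeal swab and the SST blood tube "Mandatory on day 1, optional all other days". Footnote l of the Section 4.0 test schedule adds: "Patients who are discharged prior to Day 14 will not need to come into the clinic to follow Day 1-14 Test Schedule".

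The test schedule also has a separate PCR row at Baseline and Days 7, 14, 28 and 56, which is not marked optional. Its footnote i reads "Collect nose or throat swab to measure for the presence or absence of SARS-CoV-2 by a PCR based COVID-19 test". Section 13.3.3 does not say whether this test or the Section 9 specimen supplies the clearance result.

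**The concern.** The numerator needs a documented negative result; the denominator does not need any result. A patient with no sample at a visit therefore stays below the line, cannot appear above it, and has the same effect on the rate as a patient who is still shedding.

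Missing samples after Day 1 are to be expected. They are optional, early discharge can remove the Day 7 sample, and Section 9.2.6 limits collection to Monday to Thursday (to Friday at one site). A patient whose Day 1 is a Monday reaches Days 7 and 14 on Sundays, and the schedule gives a window around those days only for stool.

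Viral clearance is the only virologic analysis that Section 13 specifies for a drug whose rationale is blocking viral entry. Readers will use it to judge whether the mechanism worked. If one arm goes home sooner, which is the hope behind objective 2.2.5, that arm could lose more Day 7 samples and look worse on clearance for that reason alone.

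**Working it through.** **Inputs.** From the documents: 132 patients per arm, two-sided 5% level (Section 13.6), and a chi-square test at each visit (Section 13.5). The documents give no sampling fraction and no expected clearance rate, so all such values below are assumptions.

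**Plan's own figure.** Section 13.6 gives no figure for clearance, only the arm size for the primary endpoint (80% vs 92%). With unpooled variance, n = (1.960 + 0.842)² × (0.80×0.20 + 0.92×0.08) / 0.12² = 127.3, so 128 per arm; with pooled variance, 131. At 132 per arm, power is 81.4% (unpooled) or 80.6% (pooled). The 132 is therefore sound as an arm size.

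**Step 1: what the formula estimates.** Let c be true clearance and s the fraction sampled, with sampling unrelated to clearance within the arm. Planned rate = c × s. With c = 70%, it reads 70%, 56%, 42% and 28% when 100%, 80%, 60% and 40% are sampled. Dividing by patients with a result gives 70% each time.

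**Step 2: equal sampling, true clearance 80% vs 60%.** With d the difference in rates, SE0 the pooled and SE1 the unpooled standard error, power ≈ Φ((d − 1.96·SE0)/SE1); the other tail is negligible here.

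- At 50% sampled, planned formula: 40% vs 30%, n = 132, SE0 = 0.0587, SE1 = 0.0584. Φ((0.10 − 0.1151)/0.0584) = Φ(−0.26) = 40%.
- At 50% sampled, patients with a result: 80% vs 60%, n = 66, SE0 = 0.0798, SE1 = 0.0779. Φ((0.20 − 0.1564)/0.0779) = Φ(0.56) = 71%.

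| Sampled in both arms | Planned formula | Patients with a result |
|---|---|---|
| 100% | 95% | 95% |
| 70% | 62% | 85% |
| 50% | 40% | 71% |

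The test keeps its 5% error rate in this setting; only power is lost.

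**Step 3: unequal sampling.** In the first three rows true clearance is the same in both arms, so every rejection is false.

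| True clearance | Sampled | Planned rates | Rejection |
|---|---|---|---|
| 80% in both | 60% vs 45% | 48% vs 36% | 51% |
| 80% in both | 60% vs 50% | 48% vs 40% | 26% |
| 70% in both | 80% vs 75% | 56% vs 52.5% | 9% |
| 80% vs 65% | 60% vs 80% | 48% vs 52% | direction reversed |

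**Step 4: sampling that depends on clearance.** Let c = 70% in both arms, with uncleared patients sampled at 80% and cleared patients at 40% vs 60%, as might follow from earlier discharge in one arm.

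- Planned rates: 0.70×0.40 = 28% vs 0.70×0.60 = 42%, a 14-point false difference, rejected about 67% of the time.
- Patients with a result: 0.28/(0.28 + 0.30×0.80) = 54% vs 0.42/(0.42 + 0.24) = 64%, a 10-point false difference, rejected about 23% of the time (about 69 vs 87 patients).

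The result-based denominator reduces this bias but does not remove it.

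**Step 5: is there a rescuing rule?** Section 13.4 excludes participants without Day 28 data, but says so for the primary endpoint. The Missing Data Considerations in Section 13.5 cover censoring of time-to-event outcomes, durations of respiratory support, and readmission. None of these reaches a per-visit proportion.

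**The case against.** The strongest reply is that the denominator wording may not be meant literally. The primary endpoint is also written over everyone in the arm (Sections 13.3.1 and 13.4), and Section 13.4 then drops patients without data. So the phrase alone does not prove that missing means failure, and neither clearance section states such a rule. This stands in part: counting missing as not cleared is a consequence of the formula as written, not an announced rule. But the primary endpoint has an exclusion sentence and clearance has none, and requiring documentation in the numerator points to the literal reading.

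Second, the scheduled PCR swab is not marked optional. A reader might infer that every virologic test after Day 1 became optional; the documents support that only for the Section 9 specimens. If the PCR test supplies the result, fewer will be missing. Any that are missing would still count as not cleared.

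Third, a reader might infer that telephone follow-up removes samples throughout. Footnote l covers only the time to Day 14, when visits resume, and footnote o is attached to physical examinations and vital signs. Discharge therefore mainly explains a missed Day 7 sample.

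Fourth, blinding makes unequal sampling less likely, and the sampling fractions used above are not in the documents. Both points are fair. Blinding does not, however, prevent unequal sampling that arises from different discharge, death or withdrawal.

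Finally, the endpoint is exploratory and feeds no sample size, interim look or stopping rule. That limits the importance of the point, not its correctness.

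**Conclusion.** The point holds. As written, the formula counts an unsampled patient as not cleared at every visit where sampling is optional (Days 7, 14, 28 and 56). Day 1 is not affected in this way, because those samples are mandatory.

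The size depends on assumed sampling and clearance. With equal sampling, the rates are too low and the comparison is diluted. A false difference needs unequal sampling: under the assumptions above, rejection with no true effect ranged from 9% (80% vs 75% sampled) to 51% (60% vs 45% sampled). Except in Step 4, the figures assume that sampling is unrelated to clearance within each arm.

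A reader might go further and infer that the rate tracks sampling rather than virus, or that the planned test is invalid in general. The documents do not support either: the rate is the product of the two, and equal sampling leaves the error rate at 5%. The primary conclusion of the trial is unaffected.

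**What to change.** Change Sections 13.3.3 and 13.5 together:

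- Use as denominator the patients with a valid result at that visit.
- State whether the Section 9 specimen or the scheduled PCR swab supplies the result.
- Report the number sampled by arm and day beside each rate.
- State how deaths before the visit are counted.
- Keep the all-patients version (missing as not cleared) and add a missing-as-cleared version, both as sensitivity bounds.

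A repeated-measures model in place of separate tests, and restriction to patients with detectable virus at Day 1, are options rather than corrections.

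The cost is SAP wording and one extra table; no new data or patients are needed. The downside is that the result-based analysis treats missing samples as ignorable. Early discharge of patients who are doing well may violate that, and Step 4 shows that part of the bias then remains. This is why the sampling table and the two bounds belong with it.
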